8. ESR

- **Sample Size:** Using the G power program for sample size calculation, setting power at 80% alpha error at 5%, reviewing results from previous studies (Danailova et al, 2022, and Bellastella et al, 2022) showed that HT patients showed a high intake of animal proteins, saturated fats, and refined sugar-in other words, the prototype of the so-called Western-type diet, in contrast with the Mediterranean one. Also, intake of the Mediterranean diet is associated with improving symptoms, assuming an effect size difference =0.5 regarding AB levels before and after dietary intervention and after a 10% adjustment for dropout rate, a sample size of at least 40 patients will be needed.
- **Sampling Method:** Convenience sampling such as that all male and female patients with HT will be invited to join the Mediterranean Diet regimen. Those who agree to participate and provide a written informed consent will be enrolled in the study.
- **Adverse events:** Possible adverse events in terms of anemia or disturbance of lipid profile will be assessed at 3 months and the patient withdrawn from the study if they occur.
- **Ethical Considerations:** A written informed consent will be obtained from each patient before enrolment in this study.

Statistical Analysis: Data will be collected and entered into the software and edited for errors. Data were expressed as median and interquartile range. Analytical statistics were done using the Wilcoxon rank test and Spearman correlation test. The Wilcoxon rank test was used to compare parameters expressed in median and IQR pre- and post-intervention. The Spearman

correlation test was used to measure the direction and strength of association between different study parameters. The P-value was used to measure the level of significance, where $P > 0.05$: non-significant (NS), $P < 0.05$: significant (S), and $P < 0.01$: highly significant (HS).

- **software to be used:** SPSS (Statistical Package for Social Sciences) version 20 will be the statistics software to be used. Citation of SPSS: IBM Corp. Released 2011. IBM SPSS Statistics for Windows, Version 20.0. Armonk, NY: IBM Corp.

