2. AIM/ OBJECTIVES

This study aims to assess the impact of Mediterranean diet on patients with Hashimoto thyroiditis using the following outcomes:

Primary outcomes: Anti-TPO antibodies, Anti-Thyroglobulin antibodies, TSH, T3, T4

Secondary outcomes: BMI, Lipid profile, Symptoms of hypothyroidism

3. METHODOLOGY:

Patients and Methods/ Subjects and Methods/ Material and Methods

- All participants will be subjected to an interview questionnaire including data pertaining name, age, sex, occupation, past medical history, 24 hours dietary recall, general clinical examination, anthropometric measures of weight, height, BMI, and biochemical Investigations including Lipid profile (Cholesterol/HDL ratio, triglycerides), HbA1C, TSH, free T3, free T4, Anti-TPO, Anti-Thyroglobulin.
- **Type of Study:** single-arm open label clinical trial
- **Study Setting:** Outpatient clinics of Ain Shams University hospitals, Cairo, Egypt.
- **Study Population:** this study will be conducted on patients with HT
- **Inclusion Criteria:**
 1. - Female and male patients with HT diagnosed by a combination of clinical features of hypothyroidism and presence of anti-thyroid antibodies.
 2. - Age from 20 to 50 years old
- **Exclusion Criteria:**
 1. -Pregnant or lactating females
 2. -Age below 20 years and above 50 years
 3. -presence of any other medical disorder
- **Pre-intervention Baseline assessment:**
 1. Anti-TPO
 2. Anti-Thyroglobulin
 3. TSH, free T3, free T4
 4. BMI (measured in kg/m²)
 5. Lipid profile (Total Cholesterol, HDL, LDL, Triglycerides)
 6. HBA1C, Fasting Blood Sugar, 2 hours Post Prandial

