 7. CBC
 8. ESR

9. Levothyroxine dose needed to reach euthyroid state

- Intervention:

The Mediterranean diet MD provides close to 30% energy from total fat (19% from MUFA, 5% from PUFA, 9% from SFA), 15% from protein and 55% energy from carbohydrate (Davis et al., 2015).

The daily caloric requirements of each individual will be set according to the age, and physical activity of the patient as per the tables in the Dietary Guidelines of the Americans, published by the United States Department of Agriculture (USDA, 2015-2020).

Reducing dietary goitrogens will be put into consideration when making meal plans.

At first there will be group sessions of 5-7 patients for 2-3 hours where Mediterranean diet and exchange lists will be explained. Then there will be a one to one (doctor to patient) 1 hour session where the 90 days program will be tailored individually to meet the nutritional requirements, food preferences and socioeconomic status of each patient. The patients will be given handouts displaying the caloric content of foods and the different exchange lists.

For the first four weeks of the program, there will be weekly 2 hour sessions. The first hour will be a group meeting where they can gain support from each other and common concerns can be clarified. Then a 1 hour one to one session will be held.

Adherence of participating cases to the diet regimen will be assessed through the recording in their handouts. Any complaint will be recorded and dealt with and any necessary modifications made.

Pre-intervention clinical and laboratory assessment done at 0 months, will be repeated at 3 months

- Study intervention period: 3 months

- Outcome:

measurement of:

1. Anti-TPO

2. Anti-Thyroglobulin
3. TSH, Free T3, Free T4

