4. BMI
5. Lipid profile (Total Cholesterol, HDL, LDL, Triglycerides)
6. Levothyroxine dose needed to reach euthyroid state
7. CBC (to check for adverse events as anemia)

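### Withdrawal for anemia or lipid disturbance is triggered only at the final visit, and the plan does not say whether those patients' data stay in the analysis

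*Combined protocol and SAP*

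**What the plan says.** - **Rule (Methodology, Adverse events).** Anemia or "disturbance of lipid profile will be assessed at 3 months and the patient withdrawn from the study if they occur".
- **Laboratory schedule (Intervention).** "Pre-intervention clinical and laboratory assessment done at 0 months, will be repeated at 3 months". No other laboratory time point is given. The weekly sessions in the first four weeks list no blood tests.
- **Length of diet.** "Study intervention period: 3 months".
- **Role of lipids (Aim/Objectives).** "Secondary outcomes: BMI, Lipid profile, Symptoms of hypothyroidism". The Outcome list names four lipid measures, and includes the blood count as the check for anemia.
- **Entry (Exclusion Criteria).** Patients are excluded for "presence of any other medical disorder". The plan does not say whether an abnormal baseline lipid counts.
- **Analysis (Statistical Analysis).** "The Wilcoxon rank test was used to compare parameters expressed in median and IQR pre- and post-intervention". Spearman correlation is the only other method. There is no analysis set, no missing-data rule, no handling of withdrawn patients, and no threshold for a lipid disturbance.

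**The concern.** A withdrawal rule protects patients when it acts while exposure can still be stopped. This one acts on a blood sample taken when the diet has already finished. What it can still change is whose data are analysed, and the plan is silent on that.

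If withdrawn patients are dropped, membership of the lipid analysis depends on the 3-month lipid value itself. With no control arm, nothing in the data would reveal the selection. The anemia and lipid events that the safety report should count would also be missing from it. Without a threshold, the decision about who is withdrawn could be made after the values are seen, still within the wording of the plan.

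**Working it through.** **The plan's own figure.** The sample size is not in dispute. A paired t test at effect size 0.5, two-sided 5%, 80% power needs 34 patients, and the Wilcoxon test (efficiency 3/π) needs 35. Dividing by 0.9 for dropout gives 38 and 39, close to the stated 40. The plan gives no figure for the withdrawal rule, so its effect has to be illustrated.

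**Assumptions (none from the plan).** Withdrawn patients' data are removed. There is one lipid, with baseline B and 3-month level F normal with SD 1 and correlation r = 0.6 or 0.8. A fixed upper limit c is exceeded by p = 20%, 10% or 5% at baseline. The true mean change is d, with positive meaning worse.

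**Entry not restricted on lipids.** Suppose everyone with F > c is removed. F − d is standard normal, so its mean among those kept is −λ(a), where a = c − d and λ(a) = φ(a)/Φ(a). B follows with slope r. Hence

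retained mean change = d − (1 − r)·λ(c − d).

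| True d | Largest distortion (p = 20%, c = 0.842, r = 0.6) | Smallest (p = 5%, c = 1.645, r = 0.8) |
|---|---|---|
| +0.3 | 0.3 − 0.4×0.488 = +0.10 | 0.3 − 0.2×0.1773 = +0.26 |
| 0 | −0.4×0.350 = −0.14 | −0.2×0.109 = −0.02 |
| −0.3 | −0.3 − 0.4×0.238 = −0.40 | −0.3 − 0.2×0.062 = −0.31 |

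Removing only the newly abnormal changes these figures by at most about 0.02 SD.

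Test behaviour was simulated with 6,000 trials of N = 40, using a two-sided 5% signed-rank test. At p = 10% and d = +0.3, detection of worsening is 22-23% with removal against 52% with everyone kept (r = 0.6), and 58-61% against 81% (r = 0.8). Over all p and r, a null diet shows false improvement in about 4-13% of trials (nominal 2.5%).

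**Entry restricted to B ≤ c.** Keeping everyone gives d + (1 − r)·λ(c), an upward shift of 0.2×0.109 = 0.02 to 0.4×0.350 = 0.14. This is regression to the mean caused by the entry rule. Under the withdrawal rule both values are cut at the same limit, so at d = 0 the bias is zero by symmetry. At d = +0.3 (simulated; numerical integration agrees to about 0.001):

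| r | p | Rule | Error | Keep all | Error |
|---|---|---|---|---|---|
| 0.6 | 20% | +0.231 | −0.069 | +0.440 | +0.140 |
| 0.6 | 10% | +0.253 | −0.047 | +0.378 | +0.078 |
| 0.6 | 5% | +0.270 | −0.030 | +0.343 | +0.043 |
| 0.8 | 20% | +0.258 | −0.042 | +0.370 | +0.070 |
| 0.8 | 10% | +0.272 | −0.028 | +0.339 | +0.039 |
| 0.8 | 5% | +0.282 | −0.018 | +0.322 | +0.022 |

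At d = −0.3 the rule gives −0.25 to −0.29 and keeping all gives −0.16 to −0.28. The rule is again closer in each cell.

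**Primary outcomes.** Selection is not on antibodies or thyroid hormones, so the direct cost of removal there is power. At effect size 0.5 (t test), 36 evaluable patients (40×0.9) give 83%, 32 give 78% and 29 give 74%. Anemia was not modelled.

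**The case against.** **Withdrawal need not mean deletion.** A reader might infer that the rule's only effect is to strip patients from the dataset. The text does not say so. The event is found in the 3-month sample, so the pre/post pair already exists when the patient is withdrawn. The blood count is listed as an outcome in order to find anemia, which would be pointless if every anemic patient were deleted. Retention is therefore a coherent reading. This stands: the documented defect is ambiguity, and the bias is conditional on removal. It does not dispose of the point, because no sentence says that the data are kept.

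**The entry criterion may already exclude dyslipidemia.** The exclusion of other medical disorders is unqualified and plausibly covers it. The rule then does little harm to the lipid estimate, and keeping everyone is further from the truth in all six cells. This also stands. A reader should not infer that removal always biases towards improvement, or that retention always gives a more accurate lipid change. Retention remains the better principle because it does not select patients on an outcome and it keeps the safety events.

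**Stronger distortions can be produced.** With a cutoff on the change rather than on the 3-month level, removing 24% of patients turns +0.30 into −0.11 SD of the change. The plan defines no such cutoff, so a reversed sign cannot be claimed.

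**The plan expects benefit.** For a true improvement of −0.3 SD with unrestricted entry, the overstatement is at most about 0.10 SD, which is modest.

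**Conclusion.** The point holds as a conditional one. The plan withdraws patients on a final-visit outcome value, when withdrawal can no longer limit exposure to the study diet, and leaves open whether their data are analysed.

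If the data are dropped and entry is not restricted on lipids, the lipid change is shifted towards benefit by about 0.02 to 0.20 SD across the three true effects examined. If entry requires normal lipids, there is no null bias and a true +0.3 SD is understated by only 0.02 to 0.07 SD. In either case, dropping these patients removes safety events from the report.

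The sizes depend on an assumed limit, correlation and single-lipid normal model. The missing retention rule and missing threshold do not. The direct bias is confined to a secondary outcome and safety reporting. The documents do not support extending it to the primary antibody and thyroid results. It should be fixed, with medium confidence in its practical importance.

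**What to change.** Replace the withdrawal sentence with:

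> Every enrolled patient with a 3-month sample stays in all pre/post analyses whether or not anemia or lipid disturbance occurred; these events are defined by a stated threshold and reported as safety outcomes (number, percentage, 95% CI); any decision to stop or change the diet is clinical care and does not affect data retention.

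Also state whether abnormal baseline lipids exclude a patient. If they do, report the lipid change with an explicit caution about regression to the mean.

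The cost is a few sentences, with no added patients, visits or assays. The downside is that lipid results may look less favourable. Under restricted entry the reported lipid change will be shifted towards worsening by +0.02 to +0.14 SD in this illustration. The caution discloses that shift but does not correct it.

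### The plan specifies no estimate of within-patient change and no confidence interval, so the before-after effect on which the trial is sized is not planned to be estimated

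*Combined protocol and SAP*

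**What the plan says.** The whole analysis plan is one paragraph, Statistical Analysis, in section 3 (Methodology). On description it says "Data were expressed as median and interquartile range". On the comparison it says "The Wilcoxon rank test was used to compare parameters expressed in median and IQR pre- and post-intervention". It adds Spearman correlations between study parameters and three significance labels, with cut-offs at P = 0.05 and P = 0.01. It does not mention a change score, an estimate of change or a confidence interval, and neither does any other section.

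Three other statements bear on this:
- Section 2 (Aim/Objectives): "This study aims to assess the impact of Mediterranean diet on patients with Hashimoto thyroiditis".
- Section 3, Type of Study: "single-arm open label clinical trial". Each patient is assessed at 0 and 3 months.
- Section 3, Sample Size: "assuming an effect size difference =0.5 regarding AB levels before and after dietary intervention", with 80% power and a 5% alpha error; then "after a 10% adjustment for dropout rate", "a sample size of at least 40 patients will be needed".

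**The concern.** With one arm and two time points, the within-patient change is the only effect measure the trial has. It is also the quantity that the sample size assumes to be 0.5 standardised units. The plan tests this change but does not say that it will be estimated. A reader could not set the result against the assumed 0.5, and a non-significant label would not separate a small change from an imprecise one.

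The planned pre and post medians do not fill the gap. Each comes from its own distribution, and the link between a patient's two values is lost. Their difference is in general neither the median of the within-patient changes nor the pseudomedian, which is what the signed-rank test addresses. An interval for the change cannot be recovered from two medians and two interquartile ranges.

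**Working it through.** **1. The plan's own figure.** Inputs from Sample Size: effect size 0.5, 80% power, alpha 5%, dropout 10%, at least 40 patients. I read 0.5 as mean change divided by the SD of the change, and the test as two-sided; the plan states neither.
- Paired t-test, noncentral t: 34 completers (power 0.808). 34 / 0.9 = 37.8, so 38 enrolled.
- Signed-rank test, efficiency 3/π for normal changes: 35 completers (power 0.801). 35 / 0.9 = 38.9, so 39 enrolled.

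Both are within two patients of 40. One-sided versions give 30 to 35 enrolled. The trial is therefore sized on a paired before-after change. With 40 × 0.9 = 36 completers, power is 83% (t) or 81% (signed-rank).

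**2. What an interval would show.** The 95% half-width for a mean change, in SDs of the change, is t(0.975; 35) / √36 = 2.030 / 6 = 0.338. If the observed effect were the assumed 0.5, the interval would run from about 0.16 to 0.84. A P label does not convey that width.

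**3. Precision of the difference between separate medians.** The documents give no SD, no SD of change and no pre-post correlation, so the correlation ρ has to be assumed. For bivariate normal data with equal SDs, the large-sample ratio of the SD of (post median − pre median) to the SD of the Hodges-Lehmann paired estimate is

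√{ (π/2)[1 − (2/π) asin ρ] / [(π/3)(1 − ρ)] }

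- ρ = 0.5: asin ρ = π/6, so √(1.047 / 0.524) = 1.41.
- ρ = 0.9: asin ρ = 1.120, so √(0.451 / 0.105) = 2.08.

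Simulation with n = 36, 20,000 trials per setting and no true change gives slightly lower values:

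| ρ | Normal data | Lognormal data, log-SD 1 (ρ on log scale) |
|---|---|---|
| 0.5 | 1.37 | 1.23 |
| 0.7 | 1.52 | 1.41 |
| 0.8 | 1.66 | 1.54 |
| 0.9 | 1.93 | 1.78 |
| 0.95 | 2.23 | 2.05 |

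The top of the range comes from antibody-like titres compared on the log scale. With a between-patient log-SD of 1.5 and a within-patient log-SD of 0.2 per measurement, ρ = 2.25 / (2.25 + 0.04) = 0.98 and the ratio is about 2.7. With 0.8 and 0.4, ρ = 0.64 / (0.64 + 0.16) = 0.80 and the ratio is about 1.7.

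**4. Direction.** With a true effect of 0.5 and n = 36, at ρ from 0.80 to 0.98 the difference of medians has the wrong sign in about 4 to 13% of trials, against 0.1 to 0.2% for Hodges-Lehmann. Among trials with a significant signed-rank result, 1.5 to 9.7% show medians moving the other way. At ρ of 0.5 to 0.7 the latter share is below 1%.

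**The case against.** The strongest reply is that nothing inferential is damaged. If the Wilcoxon test is the signed-rank form, its P-value already uses the pairing, and error rate, power and sample size stand. That is right. The loss is in what is estimated and reported.

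A reader might go further than the documents allow in three ways:
- **That the trial will yield no effect size.** The paragraph is short and silent on change scores and intervals, but it does not exclude them, and it also plans Spearman correlations. The accurate statement is that the plan specifies no estimate and no interval.
- **That the medians are about twice as noisy as a paired estimate.** No document figure supports this. Against Hodges-Lehmann a factor of 2 needs a correlation of about 0.9 or higher.
- **That medians and test will contradict each other.** Even at correlations of 0.80 to 0.98, at least 90% of significant results agree in direction, and at moderate correlations over 99% do.

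A further objection also stands. In a single-arm open-label trial an interval measures the precision of an uncontrolled change. It does not turn that change into an effect of the diet.

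**Conclusion.** The concern holds as an omission: the plan sizes the trial on a within-patient change, tests it, and does not plan to estimate it or give an interval. This part needs no assumption beyond reading the text.

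The size of the precision loss is conditional. With 36 completers, the difference of separate medians has roughly 1.2 to 1.9 times the sampling SD of the Hodges-Lehmann estimate at correlations of 0.5 to 0.9, rising to about 2.7 at 0.98. These figures rest on normal or lognormal data and on correlations that the documents do not give. The paired estimate was the more precise one at every correlation in that range. The change should be made, because the stated aim asks for a size and the data for it are already collected.

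**What to change.** Amend the Statistical Analysis paragraph as follows:

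1. Name the test as the Wilcoxon signed-rank test.
2. For each pre/post outcome, report the Hodges-Lehmann estimate of within-patient change (the pseudomedian) with its 95% confidence interval beside the P-value.
3. For anti-TPO and anti-thyroglobulin, run both the test and the estimate on log values and report a post-to-pre ratio. A ratio beside a P-value from raw values would mix two scales.
4. Base conclusions on the estimate and interval, described as uncontrolled before-after change because there is one arm.
5. Keep pre and post medians with interquartile ranges as description only.

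The cost is one extra output per variable, a log transformation for the two antibodies, and a few sentences of text. No new data are needed and the sample size does not change.
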